6.1 Treatments Administered

The selection and timing of dose for each participant is as follows:

Table 5: Selection and Timing of Dose

Study Treatment	Unit dose strength(s)/Dosage level(s)	Dosage formulation Frequency of Administration	Route of Administration
BMS-986231	12 µg/kg/min for 8 hours (20 mL/H)	Single infusion	IV
Placebo*	20 mL/H for 8 hours	Single infusion	IV
Furosemide	40 mg	Single IV bolus	IV

* Placebo will be a solution of 5% dextrose (D5W) that will be locally supplied by the site.

Restrictions related to food and fluid intake are described in Section [5.3](#).

6.2 Method of Treatment Assignment

All subjects who sign informed consent and are enrolled (including those not subsequently randomized or treated) will be assigned sequential subject numbers. Eligible subjects will be randomized according to a computer-generated randomization scheme.

If a potential subject is rescreened, a new identification number will be used.

Enrolled participants, including those not dosed, will be assigned sequential participant numbers starting with 00001, (e.g., 00001, 00002, 00003.... 00020). Those enrolled participants meeting inclusion and exclusion criteria will be eligible to be randomized. Randomization numbers will be assigned prior to dosing. Subjects who are re-enrolled (See Section [5.4](#)) will be assigned a new participant number.

Participants will not be replaced if they are discontinued from the study.

6.3 Blinding

Blinding of treatment assignment is critical to the integrity of this clinical study. However, in the event of a medical emergency or pregnancy in an individual participant in which knowledge of the investigational product is critical to the participant's management, the blind for that participant may be broken by the investigator. The participant's safety takes priority over any other considerations in determining if a treatment assignment should be unblinded.

Before breaking the blind of an individual participant's treatment, the investigator should determine that the unblinded information is necessary, ie, that it will alter the participant's immediate management. In many cases, particularly when the emergency is clearly not related to the investigational product, the problem may be properly managed by assuming that the participant is receiving active product. It is highly desirable that the decision to unblind treatment assignment be discussed with the Medical Monitor, but the investigator always has ultimate authority for the decision to unblind. The Principal Investigator should only call in for emergency unblinding AFTER the decision to discontinue the participant has been made.

In cases of accidental unblinding, contact the Medical Monitor and ensure every attempt is made to preserve the blind.

Any request to unblind a participant for non-emergency purposes should be discussed with the Medical Monitor.

In case of an emergency, the investigator may open the emergency unblinding envelope to reveal the identity of the study drug for that participant. If such unblinding occurs, the investigator shall notify the Medical Monitor immediately. This information, including the reason for the blind being broken, must be recorded on the appropriate study status page of the Case Report Form (CRF). In addition, the information that is requested on the emergency unblinding envelope must be completed.

Randomization schedules will be shipped directly to a pharmacist or other individual(s) who will be responsible for the dispensing of blinded study drug. This (these) individual(s) will be unblinded to study drug identification but will not be involved in any other aspect of study conduct. The randomization schedules will be maintained in a secure location with access limited to authorized personnel.

6.3.1 *Other Blinding and Unblinding*

The Bioanalytical Sciences section or its designate may be unblinded to the randomized treatment assignments, in order to minimize unnecessary assays of samples from subjects during the placebo treatment period. Likewise, the Metabolism and Pharmacokinetics section or its designate may be unblinded, if metabolite profiling work is conducted.

In certain circumstances, a pharmacokineticist or designate(s) in Clinical Pharmacology and Pharmacometrics, biostatistician(s) and programmer(s) at BMS, or designee, may be unblinded in order to prepare preliminary summaries of PK and safety data, as needed. These summaries will not reveal individual subjects' treatment sequence assignments.

6.4 *Dosage Modification*

BMS-986231 or placebo

The administration of the study drugs will be done through an infusion pump connected to a single peripheral IV line. After priming the infusion set tubing and connecting the lines to the IV catheter, the pump should be set to deliver the rates of infusion indicated on the infusion bag label.

The pump infusion volume display should be re-set to 0 after priming the infusion line and just prior to the start of the infusion, and the total volume infused at the conclusion of the infusion after 8 hours, or at the time of any early discontinuation, should be recorded in the clinic source documents.

[figure not shown]
At any time during the administration of study drug, the study drug infusion must be discontinued if an AE or any other safety issue suggests it is not in the patient's best interest to continue to receive study drug.

The investigator has the option to adjust the study drug dosage level downward by 50%, interrupt or discontinue the study drug infusion in patients that develop hypotension, or if the patient experiences symptomatic hypotension that is not easily tolerated, as follows (and shown in [Figure 2](#)):

- **Study drug reduction:** Study drug is decreased by 50% if SBP decreases to levels <90 mmHg but \geq 80 mmHg. The dose cannot be subsequently increased.
- **Study drug interruption:** Study drug is interrupted for 1 hour if SBP <80 mmHg or symptoms of low blood pressure occur. If the SBP is \geq 105 mmHg after one hour interruption, the study drug could be resumed at 50 % of the dose.
- **Study drug discontinuation:** Study drug will be permanently discontinued if SBP remains < 105 mmHg after 1 hour interruption or if SBP decreases to levels <80 mmHg or symptoms of low blood pressure occur.

After a dose reduction, the dose cannot be increased again. Study drug will be permanently discontinued after it has been down titrated once, and criteria for dose reduction or interruption has been met again.

If an infusion in a given period is discontinued, patients remain eligible to complete the subsequent period.

Any decision to lower the dosage level of study drug or discontinue study drug should be based on the investigator's assessment of the patient's overall clinical stability, in the context of appropriate ongoing monitoring of the patient's condition.

A 50% dosage adjustment downward will be achieved by decreasing the rate of study drug infusion from 20 mL/H to 10 mL/H.

Furosemide will be administered through an IV bolus injection at H4 of study drug infusion. In the event the study drug has been reduced, furosemide injection is administered at H4 as planned. If the study drug has been temporarily interrupted, then restarted, furosemide will be administered after at least 4 hours of effective study drug infusion.

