7 DISCONTINUATION CRITERIA

7.1 Discontinuation from Study Treatment

Participants MUST discontinue investigational product (and non-investigational product at the discretion of the investigator) for any of the following reasons:

- Participant's request to stop study treatment. Participants who request to discontinue study treatment will remain in the study and must continue to be followed for protocol-specified follow-up procedures. The only exception to this is when a participant specifically withdraws consent for any further contact with him/her or persons previously authorized by participant to provide this information.
- Any clinical AE, laboratory abnormality or intercurrent illness which, in the opinion of the investigator, indicates that continued participation in the study is not in the best interest of the participant.
- Termination of the study or the program by BMS.

- Loss of ability to freely provide consent through imprisonment or involuntarily incarceration for treatment of either a psychiatric or physical (eg, infectious disease) illness.
- If study medication has been interrupted for low blood pressure, resumed, and an episode of hypotension (or symptoms of hypotension) reoccurs.
- Occurrence of pregnancy.

Refer to the Schedule of Activities (Section 1.3) for data to be collected at the time of treatment discontinuation and follow-up and for any further evaluations that can be completed.

In the case of pregnancy, the investigator must immediately notify the Medical Monitor/designee of this event. In the event a female participant becomes pregnant during a clinical trial, the study treatment must be discontinued immediately. In most cases, the study treatment will be permanently discontinued in an appropriate manner (eg, dose tapering if necessary for participant safety). Please notify the Medical Monitor within 24 hours of awareness of the pregnancy. If the investigator determines a possible favorable benefit/risk ratio that warrants continuation of study treatment, a discussion between the investigator, the Medical Monitor/designee, and the patient must occur.

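### Protocol Section 6.4: a first episode of SBP below 80 mmHg or symptomatic low pressure meets both the interruption and the permanent-discontinuation bullet, so whether the infusion may be restarted is contradictory

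*Protocol*

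**What the plan says.** Protocol Section 6.4 (Dosage Modification) introduces the hypotension algorithm with a permissive sentence: "The investigator has the option to adjust the study drug dosage level downward by 50%, interrupt or discontinue the study drug infusion". Three bullets follow, and the text says that they are also shown in Figure 2.

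- **Reduction:** the dose is halved for SBP below 90 but not below 80 mmHg.
- **Interruption:** "Study drug is interrupted for 1 hour if SBP <80 mmHg or symptoms of low blood pressure occur". If SBP is at least 105 mmHg "after one hour interruption, the study drug could be resumed at 50 % of the dose".
- **Discontinuation:** the drug is "permanently discontinued if SBP remains < 105 mmHg after 1 hour interruption or if SBP decreases to levels <80 mmHg". The second limb reads in full: "or if SBP decreases to levels <80 mmHg or symptoms of low blood pressure occur".

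Two further rules concern repeat events. Section 6.4 adds: "Study drug will be permanently discontinued after it has been down titrated once, and criteria for dose reduction or interruption has been met again". Section 7.1 (Discontinuation from Study Treatment) lists this among the reasons for mandatory discontinuation: "If study medication has been interrupted for low blood pressure, resumed, and an episode of hypotension (or symptoms of hypotension) reoccurs".

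Section 6.4 also times furosemide. It is given at H4 if the dose was reduced. If the infusion was interrupted and restarted, it is given once at least 4 hours of effective infusion have been delivered.

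**The concern.** The interruption bullet and the second limb of the discontinuation bullet carry the same trigger and lead to different actions. Nothing in the second limb confines it to an event after a restart. A site facing a first episode therefore finds one bullet that contemplates a restart and another that rules it out.

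Hypotension is the first-listed safety endpoint (Protocol Section 9.3.3), and this algorithm is the protocol's response to it. The branch taken also reaches the efficacy data, because it decides whether the infusion resumes and, for some event times, when furosemide is given and how the urine collection is timed. SAP Section 6.2 names two sites, so different handling of the same event is a practical possibility.

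**Working it through.** The plan states no figure to reproduce here. The check is to set the triggers side by side by situation.

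| Situation | Interruption bullet | Discontinuation bullet | Repeat-event rules (6.4, 7.1) | Result |
|---|---|---|---|---|
| First fall to 80 to <90 mmHg, no symptoms | not met | not met | not met | reduction bullet alone; no conflict |
| First SBP <80 mmHg, or symptoms | met: stop 1 hour, restart possible | second limb met: permanent stop | not met | **contradiction on restart** |
| SBP <105 mmHg after the 1-hour interruption | restart condition fails | first limb met | not needed | permanent stop; no conflict |
| Repeat event after reduction or restart | met on its words if <80 mmHg or symptoms | second limb met if <80 mmHg or symptoms | met | permanent stop; settled by the repeat-event rules |

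Only the second row conflicts.

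**What the literal reading does to the other text.** The two triggers are identical, so every patient who meets the interruption bullet also meets the second limb. If that limb applies to a first episode:

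1. No patient interrupted under that bullet can reach the half-dose restart.
2. The first limb, which tests pressure after an hour's interruption, adds nothing, because the drug is already stopped for good.
3. The furosemide timing after a restart is never reached through this algorithm.
4. The Section 7.1 criterion, which needs an interruption for low pressure followed by a resumption, is never reached.

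**What the choice does to the data.** Two illustrative event times show the mechanism; they are not estimates.

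- *Event before H4, with restart.* Furosemide waits for 4 hours of effective infusion. With a 1-hour interruption, the earliest clock time is 4 + 1 = 5 hours after the start, and a 4-hour collection then runs from H5 to 5 + 4 = H9, not from H4 to H8.
- *Event before H4, no restart.* Section 6.4 gives furosemide timing for a reduced or a restarted infusion and is silent on one stopped permanently before H4.
- *Event at H6, with restart.* Furosemide has already been given and its time does not change. The infusion can resume at H7, at 10 mL/H.
- *Event at H6, no restart.* Under the footnote to Protocol Table 2, an end of infusion before H8 is an early discontinuation and the H8 assessments move to immediately after it. The void labelled H8 would then fall 6 − 4 = 2 hours after furosemide, not 4.

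**The case against.** The strongest reply is that the text is more usable than the overlap suggests. Both bullets stop the infusion immediately, so no instruction to keep infusing competes with an instruction to stop. The restart is permissive, so a site that stops and does not restart breaches neither bullet. The disputed limb also follows, in the same sentence, a clause about the period after the interruption. The repeat-event rules and the furosemide timing both presuppose that restarts happen, which suggests that the limb was meant for recurrence. The lead-in leaves room for judgement, Section 6.4 requires discontinuation whenever continuing is not in the patient's interest, and Section 8 sends immediate safety concerns to the Medical Monitor. Figure 2 is not visible here and may show the sequence clearly.

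Most of this stands, and it rules out the stronger reading that the stopping rule cannot be followed at all. It does not remove the contradiction. The surrounding text hints at a sequence, but no sentence restricts the limb, and the bullets are worded as directions despite the optional lead-in. If Figure 2 does show a clear order, the bullet would still disagree with it.

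A reader might also infer that Section 7.1 is a second contradiction, because it lists neither the failure to reach 105 mmHg nor the unqualified limb. The documents do not support that. Section 7.1 does not claim to be a complete list, and it separately covers any adverse event that, in the investigator's opinion, makes continuing not in the participant's interest. It is an incomplete cross-reference.

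**Conclusion.** The contradiction is real and narrow. For a first episode of SBP below 80 mmHg or symptoms of low pressure, Section 6.4 both contemplates and excludes a restart. The other branches can be followed. This rests on the wording of the bullets alone. It does not depend on Figure 2 and implies no view on which clinical action is right.

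The consequence is possible inconsistency between sites in restart, exposure and, depending on event time, furosemide and urine-collection timing. Its size cannot be stated. Neither document gives a rate for such episodes, and patients with SBP below 115 mmHg at screening or before randomization are excluded, with the limits checked again on each treatment day.

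A reader might infer that each episode costs 5% of the primary analysis, since 1/20 = 5%. That is only one patient's share of the planned number, not a demonstrated loss. The primary analysis uses patients who received both treatments and completed the study as per protocol (Protocol Sections 9.2 and 9.4.1.1; SAP Section 9.3). Neither document says whether a protocol-permitted discontinuation or a half-dose restart removes a patient from that set.

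**What to change.** Reconcile five places into one non-overlapping set of triggers and actions: the interruption bullet, the discontinuation bullet and the re-trigger sentence in Section 6.4, Figure 2, and the hypotension criterion in Section 7.1. Mark each trigger as applying to a first or a repeat episode. The clinical team decides which action belongs to which trigger; the statistical request is only that each situation leads to a single action.

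The cost is a clarifying protocol amendment, which under Protocol Appendix 2 includes IRB/IEC review and, where applicable, health authority approval. No design or sample-size change is needed. SAP Section 6.2 describes randomization in the past tense. If infusions have already been given, the sponsor should also record which reading each site applied to any such episode, so that the urine data from those periods can be interpreted.

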6.5 Preparation/Handling/Storage/Accountability

The investigational product should be stored in a secure area according to local regulations. It is the responsibility of the investigator to ensure that investigational product is only dispensed to study participants. The investigational product must be dispensed only from official study sites by authorized personnel according to local regulations.

The product storage manager should ensure that the study treatment is stored in accordance with the environmental conditions (temperature, light, and humidity) as determined by BMS. If concerns regarding the quality or appearance of the study treatment arise, the study treatment should not be dispensed and contact BMS immediately.

Please refer to Pharmacy Manual for additional guidance on storage of study drug. Study drug not supplied by BMS will be stored in accordance with the package insert. Please refer to [APPENDIX 2](#) for guidance on IP records and documentation.

Once study medication is reconstituted by the unblinded pharmacist, it will remain stable at room temperature for a maximum of 8 hours. Reconstituted study medication must be refrigerated immediately if dosing will not start within 1 hour.

It is recommended that study medication be removed from the refrigerator and left at room temperature for approximately 30 minutes prior to the start of the infusion.

Investigational product documentation (whether supplied by BMS or not) must be maintained that includes all processes required to ensure drug is accurately administered. This includes documentation of drug storage, administration and, as applicable, storage temperatures, reconstitution, and use of required processes (eg, required diluents, administration sets).

Storage facilities for controlled substances must be securely locked and substantially constructed, with restricted access to prevent theft or diversion, as applicable by local regulations.

Further guidance and information for final disposition of unused study treatment are provided in [APPENDIX 2](#).

6.5.1 Retained Samples for Bioavailability / Bioequivalence

Not applicable.

6.6 Treatment Compliance

Not applicable.

A series of horizontal black bars of varying lengths, likely representing data points or categories in a visualization. The bars are arranged vertically and have irregular, jagged ends, suggesting a raw or unsmoothed data set. The lengths of the bars correspond to the values of the data points, with some bars being significantly longer than others.

7 DISCONTINUATION CRITERIA

7.1 Discontinuation from Study Treatment

Participants MUST discontinue investigational product (and non-investigational product at the discretion of the investigator) for any of the following reasons:

- Participant's request to stop study treatment. Participants who request to discontinue study treatment will remain in the study and must continue to be followed for protocol-specified follow-up procedures. The only exception to this is when a participant specifically withdraws consent for any further contact with him/her or persons previously authorized by participant to provide this information.
- Any clinical AE, laboratory abnormality or intercurrent illness which, in the opinion of the investigator, indicates that continued participation in the study is not in the best interest of the participant.
- Termination of the study or the program by BMS.

- Loss of ability to freely provide consent through imprisonment or involuntarily incarceration for treatment of either a psychiatric or physical (eg, infectious disease) illness.
- If study medication has been interrupted for low blood pressure, resumed, and an episode of hypotension (or symptoms of hypotension) reoccurs.
- Occurrence of pregnancy.

Refer to the Schedule of Activities (Section 1.3) for data to be collected at the time of treatment discontinuation and follow-up and for any further evaluations that can be completed.

In the case of pregnancy, the investigator must immediately notify the Medical Monitor/designee of this event. In the event a female participant becomes pregnant during a clinical trial, the study treatment must be discontinued immediately. In most cases, the study treatment will be permanently discontinued in an appropriate manner (eg, dose tapering if necessary for participant safety). Please notify the Medical Monitor within 24 hours of awareness of the pregnancy. If the investigator determines a possible favorable benefit/risk ratio that warrants continuation of study treatment, a discussion between the investigator, the Medical Monitor/designee, and the patient must occur.

All participants who discontinue study treatment should comply with protocol-specified follow-up procedures as outlined in the Schedule of Activities, Section 1.3. The only exception to this requirement is when a participant withdraws consent for all study procedures including post-treatment study follow-up or loses the ability to consent freely (ie, is imprisoned or involuntarily incarcerated for the treatment of either a psychiatric or physical illness).

If study treatment is discontinued prior to the participant's completion of the study, the reason for the discontinuation must be documented in the participant's medical records and entered on the appropriate CRF page.

7.1.1 Post-Study Treatment Study Follow-Up

In this study, follow-up is a key endpoint of the study. Post-study follow-up is of critical importance and is essential to preserving participant safety and the integrity of the study. Participants who discontinue study treatment must continue to be followed for collection of outcome and/or survival follow-up data as required and in line with Section 4 until death or the conclusion of the study.

Participants who discontinue study treatment may continue to be followed.

